2.2.2.3 Tertiary

- Confirmation that patients on micronised progesterone have no additional clinically significant changes in their endocrine, liver function or lipid profile.
- Description of changes on CT/MRI in patients on micronised progesterone compared to those on placebo
- Acceptability/feasibility of PROMs and future trial design, including randomisation, established through patient interviews.

3. RESEARCH PLAN

3.1. Trial design

3.1.1 Patient eligibility

Major eligibility criteria will be the same in Stages 1 and 2 (see below).

Although progestins may play a role in the development of such cancers, in the context of the poor prognosis of patients with brain metastases, this risk is not clinically relevant. Moreover,

progestins have been widely used with clinical activity and benefit in patients with hormone receptor positive metastatic breast cancer.

Patients with brain metastases not infrequently present with seizures and require anticonvulsant medication. The metabolism of dexamethasone, progesterone and many of the anticonvulsants are affected by CYP450 induction/inhibition; concurrent medication will, therefore, be recorded but will not preclude study entry.

3.1.2 Inclusion Criteria

- 1) Patients ≥ 18 years' old
- 2) Capable of giving informed consent
- 3) ECOG performance status 0, 1 or 2
- 4) Clinical and/or radiological diagnosis of cerebral metastases with peri-tumoural oedema on CT/MRI in the last 14 days
- 5) Responding symptomatically to dexamethasone for control of brain tumour symptoms at a dose of $\geq 4\text{mg}-12\text{mg}$ for ≥ 48 hours
- 6) Ability to swallow oral medication

3.1.3 Exclusion Criteria

- 1) Patients who are unable or unwilling to give informed consent.
- 2) History of unexplained vaginal bleeding
- 3) Concurrent meningioma
- 4) On HRT medication
- 5) History of venous thromboembolic disease, myocardial infarction or stroke in last 12 months
- 6) History of cholestasis in the last 6 months
- 7) History of allergy to either progesterone or other ingredients of the trial drug including peanut allergy.
- 8) Pregnant or lactating (all female patients of child bearing age will undergo pregnancy testing prior to enrolment (Stage 1)/randomisation(Stage 2)
- 9) Clinically significant co-morbidities that in the opinion of the investigator would preclude study participation
- 10) Planned surgery, chemotherapy or radiotherapy within the study treatment period
- 11) Patients who have participated in Stage 1 will not be eligible for Stage 2

3.1.4 Participation in concurrent clinical trials

Patients should not participate simultaneously in more than one IMP trial at a given time; participation in a non IMP e.g. observational research could be acceptable.

3.1.5 Stage 1: Single arm, pharmacokinetic/dose confirmation

Please refer to Stage 1: Schedule of activities (Appendix 4).

We will recruit 6 evaluable patients in Leeds from whom blood samples will be collected for progesterone pharmacokinetic profiles after receiving a single oral dose of IMP (micronised progesterone) 200mg on day 1 and then a single 600mg IMP dose 5-10 days later. The daily non IMP dexamethasone dose (8mg) will be the same on both sampling days, but can be adjusted as clinically indicated between the sampling days.

Patients will be identified through site-specific teams either as an outpatient or as an inpatient. Patients will be treated and blood collected at the NIHR Leeds Clinical Research Facility. Pharmacokinetic analyses will be undertaken at the University of Bradford.

No safety issues are anticipated but patients will undergo routine clinical observations; they will not undergo any additional study specific investigations. Any patient from whom paired pharmacokinetic analyses are not obtained will be replaced. The dates and timings of pharmacokinetic sampling are shown in the Stage 1: Schedule of activities (Appendix 4).

After paired samples for 6 patients have been collected, these will be shipped to the University of Bradford for pharmacokinetic analysis. Recruitment will be suspended until pharmacokinetic analysis has been conducted.

Following pharmacokinetic analysis, if the primary endpoint is achieved a micronised progesterone dose will be selected for Stage 2 (Stage 2: Schedule of activities Appendix 5). Should the Stage 1 primary endpoint not be met, we may recruit up to 6 further evaluable patients for progesterone pharmacokinetic profiles after receiving alternative single oral micronised progesterone doses.

3.1.6 Stage 2: Randomised, double-blind, placebo pharmacokinetic/dose confirmation

Please refer to Stage 2: Schedule of activities (Appendix 5).

Please note that patients in Stage 1 are excluded from participating in Stage 2. Both are separate subsets of patients and will have a separate consent form.

We will recruit 36 evaluable patients from Leeds and Liverpool over 18 months (1 patient/month at each site), who will receive oral micronised progesterone/placebo three times a day (t.d.s.) at an initial dose determined in Stage 1; patients who are not evaluable will be replaced. The on-study starting dose of non IMP dexamethasone will be 8mg/day, which will be modified as described in Section 11.

Patients will be treated and blood collected on the NIHR Leeds Clinical Research Facility and Clatterbridge Cancer Centre, Liverpool according to the Schedule of Events. Pharmacokinetic assays and analyses will be undertaken at the University of Bradford.

Please refer to Section 11 for detail on the non IMP dexamethasone and IMP micronised progesterone/placebo dose and administration.

3.2 Pharmacokinetic (PK) sampling and analysis

Pharmacokinetic analyses will be undertaken at the University of Bradford ([name]). Levels of progesterone, dexamethasone and their metabolites will be measured by using liquid chromatography-triple quadrupole mass spectrometry (LC/MS/MS) [37,45] according to agreed SOPs (standard operating procedures) and validated methodology.

Appropriate pharmacokinetic parameters will be derived and analysed by the laboratory.

3.2.1 Timing of PK samples

3.2.1.1 Stage 1

On Day 1, and another day between Days 5 and 10, blood samples (approximately 5 mL) for pharmacokinetic analysis will be collected into heparinised tubes (BD 367874 plasma tube, sodium heparin).

These samples will be collected at baseline (pre-dosing with progesterone); then $t = 1, 2, 3, 4$ and 6 hours (all +/- 15 minutes); then 10 and 24 (both +/- 2 hours) after administration of progesterone. The timing of each sample collection will be recorded.

3.2.1.2 Stage 2

On days 1, 8 and 14 a blood sample (approximately 5 mL) will be collected into a heparinised tube (BD 367874) before the dose of progesterone and dexamethasone. The timing of sample collection will be recorded.

3.2.2 Sample processing and storage

Immediately following blood collection, the vacutainer tubes should be gently inverted 10 times. Within 30 minutes of blood collection, the sample should be centrifuged to separate the plasma (as per local protocol).

For each blood sample, the plasma layer should be transferred in roughly equal amounts to 3 labelled polypropylene tubes prior to storage. Full processing details will be provided in the Laboratory Manual.

Plasma samples for PK analysis should be stored at -80°C until shipment; storage at -20°C is acceptable if -80°C is not available.

3.2.3 Pharmacokinetic analysis

Samples will be couriered to the Clinical Trials Pharmacology Laboratory at the University of Bradford by courier; transportation boxes and dry ice will be supplied by the courier service.

3.3 Clinical and radiological assessment

Clinical review will include ECOG score and NANO scale.

Changes in cerebral oedema on imaging can be variable, difficult to demonstrate/quantify and take days to be apparent. Hence, oedema of imaging is not a reliable primary end-point to study alternatives to dexamethasone. Similarly, the heterogenous MRI scanning protocols that exist across different hospitals preclude a standardised approach to patient imaging without repeating imaging at baseline. Nonetheless, we feel it is important to measure tumour size and oedema extent at baseline (diagnosis scan) and on Day 14, in order to evaluate for any changes in these parameters, akin to the suggested guidelines specified by the RANO-BM working group (61).

Although MRI is considered the “gold standard” we recognise that its use is not universal; we permit, therefore, the use of CT at baseline to diagnose brain metastasis. The same scanning modality must be used at baseline and on Day 14.

Where MRI is undertaken at baseline and on Day 14 it will include a minimum of axial T2-weighted (or Fluid attenuated Inversion Recovery (FLAIR)), axial T1-weighted and axial T1-weighted post-gadolinium sequences, all performed at a minimum of 5 mm slice thickness. If volumetric imaging then another plane can be acquired (coronal & sagittal) and axial reconstructions provided. This will permit tumour response assessment using the RANO-BM

criteria and will allow an assessment of the extent of oedema using the system specified by Carlson et al. (62).

In those participants for whom volumetric CT/MRI data are available at both imaging time points, volumetric measurements of tumour and oedema will be made using BrainLab software. This practice is supported by the RANO-BM group: “The RANO-BM group judges that the existing data are not yet strong enough to justify the universal requirement of volumetric response criteria in clinical trials of patients with brain metastases. Volumetric analyses in real-time adds cost and complexity and is not available at all centres. Yet, RANO-BM also believes that the assessment and reporting of volumetric response in clinical trials (in addition to the unidimensional RANO-BM criteria) will add to the knowledge base, either justify or negate the need for volumetric measurements in future trials, and encourage its inclusion as a secondary endpoint when feasible.” (61)

All scans will be sent to Leeds for central review. Images will be sent via PACS transfer.

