14.4 Final analysis

The final analyses will be performed once the end of study has been declared. They will address each endpoint explicitly with evidence, including:

- Stage 1, primary endpoint (Section 2.2.1.1 Primary:) – to be assessed at end of Stage 1
 - Percentage of target exposure for each patient will be calculated and presented. Subsequent counts of number of patients to achieve 50-150% of target exposure will be presented.
- Stage 2, primary endpoint (Section 2.2.2.1 Primary:) – to be assessed at end of Stage 2
 - Number of patients tolerating progesterone until the end of the 14-day treatment period will be calculated and presented. Note that at least 13/18 patients should

be identified as tolerating progesterone (i.e., ensuring that >50% patients, using 80% CI, tolerate the treatment).

- Stage 2, secondary endpoint (Section 2.2.2.2 Secondary) – to be assessed at end of Stage 2
 - Compliance data will be presented and the number of patients complying with protocol guidelines on dose reduction will be calculated and presented. Note that at least 13/18 patients should be identified as complying with the dose reduction guidelines, to demonstrate compliance (i.e., ensuring that >50% patients, using 80% CI, comply).
 - Dexamethasone related side-effects will be coded according to the CTCAE toxicity criteria. These data will be presented in several ways, including worst value over the trial period for each patient and tabulation of all side-effects graded \geq grade 1 in at least 10% of patients.
 - Presentation/analysis of QoL (DSQ-C, EORTC QLQ-30 & BN20) data.
 - Calculation of percentage reduction in dexamethasone at Day 14.
 - Comparison of final dexamethasone dose in the progesterone and placebo arms (e.g., by ordered logistic regression).
 - Comparison of cumulative dexamethasone dose in the progesterone and placebo arms (e.g. by ANOVA/t-test or Mann Whitney U if normality assumptions are violated).
 - Comparison of time to reach final dose in each arm in the progesterone and placebo arms (e.g., Cox regression).
- Stage 2, tertiary endpoint (Section 2.2.2.3 Tertiary) – to be assessed at end of Stage 2
 - Presentation of relevant lab results to assess endocrine, liver function and lipid profiles in patients on progesterone.
 - Comparison (progesterone v placebo) of CT/MRI data (including tumour size, enhancement pattern etc)

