Appendix 5 – Stage 2: Schedule of activities

Dosing	Day -2 and -1	Day 1	Day 2	Day 3	Day 4	Day 5	Day 6	Day 7	Day 8	Day 9	Day 10	Day 11	Day 12	Day 13	Day 14	Days 15 - 21	Day 22 ⁸
Dexamethasone (mg) – non IMP	8	8	8	6 [#]	6 [#]	4 [#]	4 [#]	2 [#]	2 [#]	0 [#]	0 [#]	0 [#]	0 [#]	0 [#]	0 [#]	As clinically indicated	As clinically indicated
Micronised progesterone/ placebo t.d.s. - IMP		*	*	*	*	*	*	*	*	*	*	*	*	*	*		
Activity	Day -7 to Day -1																
Symptom directed physical examination	X	X							X						X		X
Medical History	X																
Pregnancy ⁵	X																
Neuro. exam ¹		X							X						X		X
Weight/BMI		X							X						X		X
BP, pulse, temp		X							X						X		X
AE review and Dex/IMP dose review	X		X		X		X		X		X		X		X	X ⁷	X
Concomitant Medications Review	X	X							X						X		X
Full blood count	X	X							X						X		X
Clotting profile	X	X							X						X		X
U & E, LFT, Ca	X	X							X						X		X
Hormone profile ²		X													X		

Progesterone/placebo PK blood samples ³		X							X						X		
Side-effects diary		X	X	X	X	X	X	X	X	X	X	X	X	X	X	X	X
Patient Interview ⁴																X	
DSQ-C		X													X		
EORTC QLQ-C30		X													X		
EORTC BN20		X													X		
CT/MRI brain ⁶	X														X		

On Day 3 to day 14, if clinically appropriate, the dexamethasone dose will be reduced by 2mg/day on alternate days and can be discontinued if indicated. See Appendix 7 Drug Table Stage 2 for further detail

* Dose determined in Stage 1 and modified as per protocol

¹ Neurological assessment will also be completed at any time dexamethasone dose needs to be increased

² Patient will be asked to fast (water only) and avoid taking their dexamethasone and progesterone/placebo before the blood sample is taken between 8.00am – 10.00am. After which they should take their prescribed dexamethasone and progesterone/placebo. "Hormone bloods" include: cortisol, glucose, testosterone, lipids; HbA1c, TSH, free T4, FSH, LH, oestrogen, IGF-1.

³ Trough progesterone and dexamethasone levels. Prior to dose of progesterone (or placebo) and dexamethasone. These will be between 8.00am-10.00 am where the patients will already be delaying taking the medication.

⁴ To be completed once between Day 15 and Day 21. Approximately 15 patients will be approached for the patient interview.

⁵ WOCBP – Woman of child bearing potential only

⁶ CT/MRI brain – Within 14 days of screening visit.

⁷ Alternate days.

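### The MRI rule sets 5 mm as a minimum slice thickness and binds a baseline scan the trial does not control, while contrast and thickness are not matched across scans where the comparison needs it (minor)

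*Protocol*

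**What the plan says.** Protocol 3.3 sets the acquisition rule for MRI. It opens "Where MRI is undertaken at baseline and on Day 14 it will include a minimum of axial T2-weighted" (or FLAIR), adds axial T1 and post-gadolinium axial T1, and closes with "all performed at a minimum of 5 mm slice thickness". No maximum thickness appears anywhere. The next sentence begins "If volumetric imaging then another plane can be acquired" and asks for axial reconstructions. BrainLab volumes are planned for patients with volumetric data at both time points.

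The same section says the purpose is to "measure tumour size and oedema extent at baseline (diagnosis scan) and on Day 14", so baseline is a scan taken for diagnosis. It also says that differing hospital protocols "preclude a standardised approach to patient imaging without repeating imaging at baseline". Section 3.1.2 accepts "Clinical and/or radiological diagnosis of cerebral metastases with peri-tumoural oedema on CT/MRI in the last 14 days". Appendix 5 has one pre-treatment imaging entry, with the footnote "CT/MRI brain – Within 14 days of screening visit".

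CT is allowed, and the modality must be the same at both time points. Nothing is said about contrast or slice thickness for CT. All scans are read centrally in Leeds.

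The scans serve a tertiary aim (2.1.3: no undesired change in tumour size or enhancement pattern) and a tertiary descriptive endpoint (2.2.2.3). Section 14.4 Final analysis lists "Comparison (progesterone v placebo) of CT/MRI data (including tumour size, enhancement pattern etc").

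**The concern.** A slice-thickness rule exists to secure resolution, so it should cap thickness. This one sets a floor. A site following the words may scan at 6, 8 or 10 mm and may not use 3 mm.

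The rule also prescribes how the diagnosis scan is acquired, after that scan has usually been taken. The protocol does not say whether a patient whose diagnosis MRI breaks the rule is rescanned, left out of the imaging comparison or analysed anyway.

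The imaging check rests on within-patient change in at most about 18 patients per arm. Coarse or mismatched slices add noise to apparent size change. A CT pair with contrast at only one time point cannot show a change in enhancement. Neither fault can be repaired once the Day 14 scan has been taken.

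**Working it through.** **Plan's own figures.** The protocol gives no imaging figure to reproduce. Its only design figures concern Day 14 dexamethasone dose. They reproduce (18 per arm, one-sided 0.05, noncentral t: 90.2% at effect size 1.00 and 80.3% at 0.85, against the stated 90% and 80%) and have no bearing here.

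**What must match between the two scans (3.3).**

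| | MRI pair | CT pair |
|---|---|---|
| Modality | same at both | same at both |
| Sequences | specified at both | not applicable |
| Contrast | gadolinium T1 at both | not specified |
| Slice thickness | 5 mm floor, no cap, no matching | not specified |

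An enhanced diagnosis CT followed by an unenhanced Day 14 CT therefore complies. So does a 5 mm MRI followed by a 7 mm MRI.

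**Baseline.** Section 3.3 says standardisation needs a repeat baseline scan. Section 3.1.2 and Appendix 5 accept an existing scan and schedule no repeat. Section 3.3 nevertheless applies its sequence and thickness rule to baseline.

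**Size, by assumption.** The documents give no lesion sizes or scanner settings. Take a sphere of radius R cut by contiguous slices of thickness T and read at slice centres.

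In the worst case the nearest slice centre lies T/2 from the equator, so the measured diameter is d = 2√(R² − (T/2)²).

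- 10 mm lesion: T = 5 gives 2√(25 − 6.25) = 8.66 mm (13% low); T = 8 gives 2√(25 − 16) = 6.0 mm (40% low).
- 20 mm lesion: T = 5 gives 2√(100 − 6.25) = 19.36 mm (3% low); T = 8 gives 2√(100 − 16) = 18.33 mm (8% low).
- 30 mm lesion: T = 5 gives 2√(225 − 6.25) = 29.58 mm (1% low); T = 8 gives 2√(225 − 16) = 28.91 mm (4% low).

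Within-patient change is the relevant quantity. The table gives the 95th percentile of the absolute apparent change in largest in-plane diameter. It assumes two scans of equal thickness, independent random offsets (50,000 simulated pairs) and no true change.

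| Lesion | 3 mm | 5 mm | 7 mm | 10 mm |
|---|---|---|---|---|
| 10 mm | 4% | 12% | 27% | breaks down (about 160%) |
| 15 mm | 2% | 5% | 10% | 24% |
| 20 mm | 1% | 3% | 5% | 12% |
| 30 mm | <1% | 1% | 2% | 5% |

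Unequal thickness also shifts the average. Mean reading as a fraction of true diameter, for 5 mm and 7 mm slices, is 0.957 and 0.911 (10 mm lesion), 0.990 and 0.979 (20 mm), and 0.995 and 0.991 (30 mm). A 5 mm baseline followed by a 7 mm Day 14 scan gives an average apparent shrinkage of 1 − 0.911/0.957 = 4.8%, 1 − 0.979/0.990 = 1.1% and 1 − 0.991/0.995 = 0.4%.

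Volumes from summed slice areas do not worsen steadily with thickness in this model (10 mm lesion: 34% at 5 mm, 15% at 7 mm). The plan takes volumes only from volumetric pairs, so I do not rely on them.

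**The case against.** The strongest reply is that the intent is plain. The same sentence uses its minimum wording for the required sequence set, in the sense of a minimum standard, and a true 5 mm floor would defeat the volumetric imaging that follows. That is probably right. It makes this a wording slip, but sites act on the words and nothing else in the protocol corrects them.

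The protocol also discloses that imaging cannot be standardised and is not a reliable primary endpoint. It requires one modality per patient, reads scans centrally and plans no formal efficacy comparison (11.8). This lowers the stakes. Central review standardises the reading, though, and leaves acquisition as it was.

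A reader might infer more than the documents support:

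- **That modality is the only link between the two scans.** For MRI, sequences and gadolinium are required at both. The contrast gap is confined to CT.
- **That a 1 mm baseline followed by a 6 mm Day 14 scan simply complies.** Under the literal floor a 1 mm scan breaches the rule. The pair passes only through the volumetric allowance.
- **That the error is as large as the change sought.** The protocol states no target imaging change.
- **That the arms are compared unfairly.** Allocation is blinded, 1:1 and stratified by site, so acquisition error should fall on both arms alike. It adds noise and, with mismatched thickness, a shift expected to be common to both arms.
- **That the sites will use very thick slices.** Nothing in the documents says so.

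**Conclusion.** The point holds and is minor. The slice rule is worded in the wrong direction, and read literally it conflicts with the volumetric option beside it. It is also applied to a diagnosis scan that the same section says cannot be standardised without a repeat. Thickness is not matched for MRI. Neither thickness nor contrast is fixed for CT, although enhancement pattern is to be compared.

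The size of the resulting error cannot be derived from the documents. Under an idealised sphere read at slice centres, it is material for lesions of about 10 mm with slices thicker than 5 mm and small for lesions of 20 to 30 mm. No primary or secondary endpoint uses these scans; what is affected is a tertiary, descriptive safety check.

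**What to change.** In 3.3:

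1. Word the limit as a slice thickness no greater than 5 mm.
2. Apply the acquisition rule to the Day 14 scan. Match that scan, as far as possible, to the patient's own diagnosis scan in plane, contrast use and thickness, up to that maximum. Cover CT as well as MRI.
3. Have central review record slice thickness and contrast use for both scans, so that pairs that could not be matched (for example a diagnosis scan thicker than 5 mm) are visible.
4. Compare enhancement pattern only in pairs where both scans were contrast-enhanced, and report how many pairs that leaves.

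The cost is wording in 3.3 and in the imaging instructions to two sites, with no extra scan or reader. Some pairs will be declared not assessable for enhancement. The cap does not remove all error: in the idealised model a 10 mm lesion can still read up to 13% low at 5 mm slices.

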3.4 Patient reported outcome measures (PROMS)

Patients in Stage 2 will report their QoL using PROMS and have their symptom burden assessed using mixed quantitative and qualitative methodologies.

3.4.1 Validated questionnaires

In concordance with the RANO recommendations (5) we will use a combination of patient reported outcome measures. The Dexamethasone Symptom Questionnaire-Chronic (DSQ-C) [2,3] will be used to assess side-effects related to dexamethasone use, the EORTC Quality of Life Questionnaire Core 30 (EORTC QLQ-C30) [1] and Brain Cancer Module (EORTC BN20) [40] to assess generic and disease-specific QoL, respectively. Single items to assess micronised progesterone related side-effects, and side-effects that might result from drug interactions (e.g., with antiepileptic drugs), will be added from the EORTC item bank library (e.g. “have you had pain in your stomach area?”, “have you had a rash?”). These PROMs are widely used, have good psychometric properties and are validated in the relevant patient population. Completion is facilitated by use of the same scale (ranging from 1: ‘not at all’ to 4: ‘very much’) and the same recall period (past week). If necessary, patients can be assisted by a researcher or their caregiver in completing the questionnaires. Completion should take less than 15 minutes.

